## 9. Tests/Observations

### 9.1 Test/Observation Schedule

#### (1) Cohort 1

Day of consent	Visit 1		Visit 2		Visit 3		Visit 4	Visit 5		Visit 6	At discontinuation
	1st vaccination	2nd vaccination	3rd vaccination				Post-vaccination Examination 1	4th vaccination	Vaccination		
	Before	After	Before	After	Vaccination	Before	After	Before	After		
Allowable Window	D1		Visit 1 + 3 - 8 weeks		Visit 2 + 3 - 8 weeks		Visit 3 + 4 - 6 weeks	Visit 3 + 6 - 13 months		Visit 5 + 4 - 6 weeks	
Written informed consent	•										
Investigation of subject background		•							•		
Examination	•	•	• *1	•	• *1	•	• *1	•	•	• *1	•
Body temperature measurement (axillary)	•		•		•				•		
Investigational product vaccination		•		•			•		•		
Blood sampling (antibody titer)	•							•	•	•	• *2
Adverse events *3			◀			▶					
e-Diary *4			•		•		•		•		

\*1: Subjects will be asked to wait in the hospital for 30 minutes after receiving the investigational product, and will be examined 30 minutes after vaccination.

\*2: Blood samples will be collected for antibody titer measurement only at discontinuation after the third or fourth dose of the investigational product has been administered.

\*3: An investigation will be performed to confirm whether or not the subject experienced any adverse events during the period from Visit 1 to Visit 4, and during the period from Visit 5 to Visit 6, based on examination of the subject at the study visits and based on the subject's e-Diary. Only serious adverse events will be investigated during the period from Visit 4 to Visit 5.

\*4: Every day until 14 days after each dose, if the subject's symptoms have not returned to normal by Day 14 after vaccination with the investigational product, then the legal guardian will be asked to, as a rule, fill out the e-Diary until the symptoms return to normal.

(2) Cohort 2

	Day of consent	Visit 1		Visit 2		Visit 3		Visit 4		At discontinuation	
		1st vaccination		2nd vaccination		3rd vaccination		Post-vaccination Examination 1			
		Before	Vaccination	Before	Vaccination	Before	Vaccination	After	After		
Allowable window		D1		Visit 1 + 3 - 8 weeks		Visit 2 + 3 - 8 weeks		Visit 3 + 4 - 6 weeks			
Written informed consent	•										
Investigation of subject background		•									
Examination	•		• 	•		• 	•		• 	•	
Body temperature measurement (axillary)		•		•			•				
Investigational product vaccination			•		•			•			
Blood sampling (antibody titer)		•							•	• 	
Adverse events 				↔							
e-Diary 				•		•		•			

\*1: Subjects will be asked to wait in the hospital for 30 minutes after receiving the investigational product, and will be examined 30 minutes after vaccination.

\*2: Blood samples will be collected for antibody titer measurement only at discontinuation after the third dose of the investigational product has been administered.

\*3: An investigation will be performed to confirm whether or not the subject experienced any adverse events during the period from Visit 1 to Visit 4 based on examination of the subject at the study visits and based on the subject's e-Diary.

\*4: Every day until 14 days after each dose, if the subject's symptoms have not returned to normal by Day 14 after vaccination with the investigational product, then the legal guardian will be asked to, as a rule, fill out the e-Diary until the symptoms return to normal.

(3) Cohort 3

	Day of consent	Follow-up blood sample
Written informed consent obtained	•	
Blood sampling (antibody titer)		• 

\*1: For subjects from whom written informed consent has been obtained only, and after the end of Cohort 2, and generally for 4 or more weeks after the administration of the booster immunization as part of, for example, routine immunization, the (sub)investigator will perform antibody titer measurements as a follow-up investigation, depending on the results obtained after the primary immunization in Cohort 2, or in accordance with the wishes of the subject (subject's legal guardian).

## 9.2 Test/Observation Parameters and Time Points

### 9.2.1 Subject Characteristics

The (sub)investigator will investigate the following subject characteristics and record the results in the case report form.

- (1) Sex
- (2) Date of birth (Western calendar)
- (3) Complications (at the time of the first dose of the investigational product)

Investigation time point: The day of the first vaccination with the investigational product

### 9.2.2 Vaccination Status

The (sub)investigator or a clinical research coordinator will record the following information in the case report form.

- (1) Drug number
- (2) Day of vaccination with investigational product
- (3) Body temperature (axillary) prior to vaccination with the investigational product
- (4) Site of vaccination with the investigational product
- (5) Status of simultaneous immunization with a vaccine other than the investigational product (day of vaccination, type of vaccine simultaneously administered, site of vaccination)

### 9.2.3 Efficacy Endpoints

#### 9.2.3.1 Antibody Titers

The (sub)investigator or a clinical research coordinator will take blood samples at the following time points in order to measure the subject's antibody titers. More detailed information is provided in the separate "Clinical Study Testing Procedures." The (sub)investigator will record the days of blood sample collection (except for those in Cohort 3) in the case report form.

- (1) Sample Collection
  - 1) Times of blood sample collection, and volume of the sample collected, in Cohort 1
    - (a) Times of blood sample collection: Before the first vaccination with the investigational product, at Post-vaccination Examination 1, before the vaccination of the fourth dose of the investigational product, at Post-vaccination Examination 2, or at discontinuation (only when discontinuation occurs after the vaccination of the third or fourth dose of the investigational product)  
Volume of blood collected: Around 3 mL, as a rule
    - (b) Number of samples collected: 4
  - 2) Times of blood sample collection, and volume of the sample collected, in Cohort 2
    - (a) Times of blood sample collection: Before the first vaccination with the investigational product, at Post-vaccination Examination 1, or at discontinuation (only when discontinuation occurs after the vaccination of the third dose of the investigational product)  
Volume of blood collected: Around 3 mL, as a rule
    - (b) Number of samples collected: 2
  - 3) Times of blood sample collection, and volume of the sample collected, in Cohort 3

(a) Times of blood sample collection: Blood samples will be collected, as a rule, after 4 weeks have passed since the administration of the booster immunization.

Volume of blood collected: Around 3 mL, as a rule

(b) Number of samples collected: 1

4) Blood processing

The blood will be processed as described separately in the "Clinical Study Testing Procedures."

(2) Shipment of samples

The samples (serum) for antibody titer measurement will be collected by the antibody titer measurement sample transportation organization, and sent to the antibody titer measurement organization as described separately in the "Clinical Study Testing Procedures."

(3) Measurement parameters

Hib	Anti-PRP antibody concentration
Diphtheria	Anti-diphtheria antibody concentration
Pertussis	Anti-pertussis antibody concentration
	Anti-FHA antibody concentration
Tetanus	Anti-tetanus antibody concentration
Polio	Attenuated anti-poliovirus antibody titers* (types 1, 2, and 3)

\*: Sabin strains

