### 12.2 Discontinuation Procedures

If a subject is discontinued from the study during the term of the study, the (sub)investigator will take whatever actions are appropriate for the subject, and will inform the monitor in question that the subject has been discontinued from the study.

The day of study discontinuation will be the day on which the (sub)investigator made the decision to discontinue the subject from the study.

The (sub)investigator will perform follow-up by examining the subject as much as possible to investigate the presence or absence of adverse events in the 2 weeks after vaccination with the investigational product (in the period up until the day of discontinuation if the day of discontinuation is more than 2 weeks after vaccination with the investigational product). If the subject is discontinued from the study after the third or fourth dose (except for subjects discontinued in the period from after Post-vaccination Examination 1 to before the fourth vaccination), blood samples for antibody titer measurement will be collected whenever possible 4 to 6 weeks after vaccination. If a subject has not completed all of the vaccinations, the subject's legal guardian will be given a full explanation of the vaccinations that the subject will receive after the subject has been discontinued from the study.

The concomitant medications will be confirmed at discontinuation, at the time of blood sample collection (except for Cohort 3), or at 2 weeks after vaccination, whichever comes last.

The (sub)investigator will record the day of discontinuation and the reason for discontinuation\* in the case report form.

For subjects for whom the specified observations/tests cannot be performed at discontinuation, or who did not come in for any study visits after discontinuation, the reasons for this, the subject's subsequent course, etc. will be followed up either in writing (correspondence) or by telephone or the like.

If the subject does not come in for a visit, the (sub)investigator or a clinical research coordinator will ask the subject's guardian to fill out the e-Diary as much as possible.

\*: The "reason for discontinuation" will be selected from among the following.

1. Adverse event
2. Death

3. Clearly unsuitable as a subject for the study
4. Study protocol deviation
5. Technical problem
6. Subject's legal guardian requested discontinuation

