2.4. Assessment Time Point

The Cohort 2 assessment time points are shown below.

Day of consent	Visit 1		Visit 2		Visit 3		Visit 4		At discontinuation
	1st vaccination	2nd vaccination	3rd vaccination	Vaccination	Post-vaccination Examination 1				
Before	After	Before	After	Before	After	Before	After		
Allowable window	D1		Visit 1 + 3 - 8 weeks		Visit 2 + 3 - 8 weeks		Visit 3 + 4 - 6 weeks		
Written informed consent	•								
Investigation of subject background	•								
Examination	•		• ¹	•	• ¹	•	• ¹	•	•
Body temperature measurement (axillary)	•			•		•			
Investigational product vaccination		•			•		•		
Blood sampling (antibody titer)	•							•	• ²
Adverse events ³			↔						
e-Diary ⁴			•		•		•		

*1: Subjects will be asked to wait in the hospital for 30 minutes after receiving the investigational product, and will be examined 30 minutes after vaccination.

*2: Blood samples will be collected for antibody titer measurement only at discontinuation after the third dose of the investigational product has been administered.

*3: An investigation will be performed to confirm whether or not the subject experienced any adverse events during the period from Visit 1 to Visit 4 based on examination of the subject at the study visits and based on the subject's e-Diary.

*4: Every day until 14 days after each dose, if the subject's symptoms have not returned to normal by Day 14 after receiving the investigational product, then the subject will be asked to, as a rule, fill out the e-Diary until the symptoms return to normal.

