6.2. Allowable Assessment Time Point Deviation Window

For the tabulation at each time point of test and observation parameters, data meeting the allowable time window in days specified in “9.1 Test/Observation Schedule” of the study protocol will be used, and data will not be replaced using data from outside the allowable windows.

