7.1.6. Tabulation Time Points and Baselines

The tabulation time points will be displayed as shown in the table below. The baseline will be “Before the first dose at Visit 1.”

Table 7.1.5: Tabulation Time Points

Notation for Tabulation		Assessment Time Points in the Protocol
Assessment Time Point	Abbreviation	
Before the first vaccination	V1	Before the first dose at Visit 1
4 weeks after the primary immunization	V4	Post-vaccination examination at Visit 4, and at discontinuation

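### The protocol gives two sampling times for the discontinuation titer, and neither SAP time-point table says when such a titer counts as post-primary or post-booster

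*Protocol*

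**What the plan says.** **When blood is drawn.** For Cohort 2, protocol 9.2.3.1 lists a sample "at discontinuation (only when discontinuation occurs after the vaccination of the third dose of the investigational product"). Note 2 to the Cohort 2 schedule in 9.1 agrees: "Blood samples will be collected for antibody titer measurement only at discontinuation after the third dose of the investigational product has been administered". The synopsis schedule and the Cohort 2 SAP schedule (2.4) repeat that note. The Cohort 1 versions, in the protocol and in the Cohort 1 SAP (2.4), say the same for discontinuation after dose 3 or dose 4. None sets a minimum interval after the dose.

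Protocol 12.2 differs. For infants leaving after dose 3 or 4, "blood samples for antibody titer measurement will be collected whenever possible 4 to 6 weeks after vaccination". It exempts those who leave after Post-vaccination Examination 1 and before dose 4. It also fixes the discontinuation date: "The day of study discontinuation will be the day on which the (sub)investigator made the decision to discontinue the subject from the study".

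**How the titer is tabulated.** In the Cohort 2 SAP, Table 7.1.5 gives the source of V4, the four-week post-primary time point, as "Post-vaccination examination at Visit 4, and at discontinuation". SAP 6.2 limits tabulation to data inside the protocol 9.1 windows and adds that "data will not be replaced using data from outside the allowable windows". The Visit 4 window is "Visit 3 + 4 - 6 weeks"; the discontinuation column has none. In the Cohort 1 SAP, Table 7.1.5 attaches discontinuation to V6, the four-week post-booster time point, and to nothing else.

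**The concern.** The day of a withdrawal decision can fall anywhere after dose 3. A site working from the schedule or from 9.2.3.1 may bleed the infant that day; a site working from 12.2 would wait until weeks 4 to 6. The SAP does not settle what happens to the early titer.

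In Cohort 2 this titer feeds the primary seroprotection rates and the geometric means. If it is counted, a value from a few days after dose 3 is reported as a four-week value and may understate the response. If it is dropped, an infant with no other post-primary titer leaves the FAS, about 3 mL of blood was taken for a result that is not tabulated, and the sample that 12.2 asks for was not obtained. In Cohort 1, a titer from an infant who never had a booster can carry the post-booster label.

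**Working it through.** The plan states no figure for this point. The 170 per group cannot be re-derived, since no expected rate, precision target or dropout rate is given. The check is to follow the text, then gauge scale.

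**Are the two sampling times really different dates?** Yes. Protocol 12.2 says concomitant medications are "confirmed at discontinuation, at the time of blood sample collection (except for Cohort 3), or at 2 weeks after vaccination, whichever comes last". That sentence makes sense only if discontinuation and blood sampling can fall on different days.

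**Three example infants**

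| Case | 9.1 and 9.2.3.1 | 12.2 | SAP time point |
|---|---|---|---|
| Cohort 2, withdrawn 5 days after dose 3 | Draw on day 5 | Draw at weeks 4 to 6 | V4, no time condition |
| Cohort 1, withdrawn 5 days after dose 3 | Draw on day 5 | Draw at weeks 4 to 6 | V6 (post-booster) |
| Cohort 1, withdrawn between Visit 4 and dose 4 | Draw at discontinuation | Exempt | V6 (post-booster), if drawn |

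**The Cohort 2 day-5 titer under SAP 6.2**

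- If the Visit 4 window is taken to govern V4, day 5 is outside it and the titer is not tabulated. With no other post-primary titer, the infant is excluded from the FAS (SAP 5.1).
- If the discontinuation column is taken to have no window, nothing removes the titer and it enters SAP 7.5.1 and 7.5.2.2.
- A draw at weeks 4 to 6 after dose 3 meets the Visit 4 window, and the question does not arise.

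**Scale in Cohort 2.** Inputs: n = 170 per group (SAP 2.5). Assumptions: true rate p of 90% or 95%, and k early titers in one group, all counted and all below threshold (the worst case). The shift in that group's rate is (n − k)p/n − p = −kp/n, so it can never exceed 1/170 = 0.59 points per infant.

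| k (share of group) | Shift at p = 90% | Shift at p = 95% | Denominator if dropped |
|---|---|---|---|
| 1 (0.6%) | −0.53 | −0.56 | 169 |
| 2 (1.2%) | −1.06 | −1.12 | 168 |
| 4 (2.4%) | −2.12 | −2.24 | 166 |
| 9 (5.3%) | −4.76 | −5.03 | 161 |

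For comparison, the Clopper-Pearson 95% interval is 84.5% to 94.1% for 153/170 and 90.9% to 97.9% for 162/170, so 9.6 and 7.0 points wide. A simple normal approximation, 1.96 × √(2p(1 − p)/170), puts the half-width for the group difference at 6.4 points (p = 90%) and 4.6 points (p = 95%).

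**The case against.** The strongest reply is that the passages can be read together. Section 9.2.3.1 and the schedule notes may be saying who is sampled, and 12.2, the section devoted to discontinuation, when. Cohort 2 infants have two samples in total, which suggests that the discontinuation sample takes the place of the Visit 4 sample. On that reading Table 7.1.5 of the Cohort 2 SAP is sensible: it lets an in-window sample from a withdrawn infant count as V4. Protocol 9.2.3.1 also defers detail to separate testing procedures, and the sponsor may settle subject-handling rules before database lock.

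Much of this stands. If every site follows 12.2, the Cohort 2 timing problem largely disappears. It does not remove the conflict, because the schedule and the sampling section carry neither the timing nor the exemption, and a site can comply with them as written and draw too early. Nor does it touch the Cohort 1 assignment to V6 alone.

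A reader might infer that every Cohort 2 discontinuation titer will be counted as a four-week result and will bias the primary endpoint. The documents do not support that. SAP 6.2 and protocol 13.2.2 more plausibly exclude an out-of-window titer, and the V4 label itself points to the Visit 4 window. That an early titer mostly reflects two doses is also an inference; the documents give no response after dose 2.

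**Conclusion.** The inconsistency is real. The protocol gives two sampling times for one titer and two rules for Cohort 1 infants who leave between Post-vaccination Examination 1 and dose 4. The Cohort 2 SAP leaves open whether an early titer is counted or, more plausibly, dropped. The Cohort 1 SAP would label a titer as post-booster in an infant who had no booster.

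The effect on the Cohort 2 results is probably small. It concerns only infants who leave between dose 3 and Visit 4, and each moves a group rate by at most about 0.6 points. Shifts of several points need several such infants in one group, all sampled early, counted and below threshold; the documents give no dropout rate to support any particular number. If both groups are affected, the shifts partly cancel in the difference. The study is exploratory and sets no significance level. The reason to act is that a missed 4 to 6 week sample cannot be recovered and that the repair is cheap.

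**What to change.** - **Protocol:** reconcile note 2 of the synopsis and 9.1 schedules (Cohorts 1 and 2), and 9.2.3.1, with the sampling time and the exemption in 12.2. The 12.2 timing matches the Visit 4 window.
- **SAP schedules:** make the same change to note 2 in section 2.4 of both cohort plans.
- **Cohort 2 SAP, Table 7.1.5:** count a discontinuation titer as V4 only if it falls 4 to 6 weeks after Visit 3.
- **Cohort 1 SAP, Table 7.1.5:** assign a discontinuation titer to V4 or V6 by the last dose received, with the same 4 to 6 week window after that dose.
- **Both SAPs:** list all other discontinuation titers without tabulating them.

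The cost is wording in the protocol and two SAP tables with their schedule notes. The downside is small: some withdrawn infants will not return at weeks 4 to 6 and will have no tabulated titer.

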## 9.2.4 Safety Endpoints

### 9.2.4.1 e-Diary

The (sub)investigator or a clinical research coordinator will have the legal guardian enter information for the following parameters in the e-Diary every day until Day 14 after vaccination with the investigational product, and if the subject's symptoms have not resolved by Day 14 after vaccination with the investigational product, then the legal guardian will, as a rule, be asked to enter this information until the symptoms resolve.

- (1) Body temperature (axillary)
- (2) The presence or absence of investigational product (investigational substance or control substance) vaccination site reactions (redness, swelling, induration, pain), and size (redness, swelling, induration) or severity thereof
- (3) The presence or absence of systemic reactions (irritability, crying, decreased appetite, decreased sleep, increased sleep), and the severity thereof

### 9.2.4.2 Adverse Events

An adverse event is any clinically undesirable or unintended sign (including clinically significant test value abnormalities), symptom, or disease that occurs during the safety assessment period following vaccination with the investigational product, regardless of whether or not it is causally related to the investigational product.

Furthermore, vaccination site reactions (redness, swelling, induration, pain) and systemic reactions (pyrexia, irritability, crying, decreased appetite, decreased sleep, increased sleep), which are reactions that are specific to vaccination, that occur in the period up through Day 14 after vaccination with the investigational product will be considered pre-specified adverse events. Vaccination site reactions to other

vaccines that were administered at the same time will be considered normal adverse events, and will not be considered pre-specified adverse events. Axillary body temperature  $\geq 37.5^{\circ}\text{C}$  will be handled as the adverse event “pyrexia.” In addition, adverse events that occur within 30 minutes after vaccination with the investigational product will be considered immediate reactions.

(1) Symptoms or diseases

The (sub)investigator will confirm the presence or absence of adverse events based on the contents of the e-Diary that has been filled out by the legal guardian, as well as by questioning of the legal guardian and observation of the subject.

(2) Clinical laboratory test abnormalities

The (sub)investigator will handle as an adverse event any event that is judged to be a clinically significant abnormality.\*

\*: A “clinically significant test value abnormality” will be determined based on the following criteria.

- When there is a relationship to a clinical sign or symptom

However, if these symptoms or signs have been reported as separate adverse events, then there is no need to handle this test value abnormality as an adverse event.

- When a medical or surgical treatment has been administered for the test value abnormality in this clinical laboratory tests
- When the investigational product vaccination method has been changed (e.g., a change in the dose, treatment interruption, treatment discontinuation) because of the test value abnormality
- When the (sub)investigator determines for some other reason that the finding is a clinically significant abnormality

(3) Safety assessment period

1) Cohort 1

The period from the first vaccination with the investigational product until Post-vaccination Examination 2 will be considered the safety assessment period. However, the collection of all adverse events will be performed for the period from the first vaccination with the investigational product until Post-vaccination Examination 1, and also for the period from the vaccination of the fourth dose of the investigational product until Post-vaccination Examination 2. Additionally, information about serious adverse events will be collected throughout the entire safety assessment period.

2) Cohort 2

The period from the first vaccination with the investigational product until Post-vaccination Examination 1 will be considered the safety assessment period, and all adverse events and serious adverse events will be collected.

(4) Adverse event assessment and criteria

1) Day of onset

The day of onset will be the day on which the symptom is observed or the day on which the clinical test value abnormality was observed.

